The purpose of this single blinded, randomized, controlled, superiority trial is to compare the efficacy of an ultrasonic bone scalpel with standard of care surgical instruments during posterior spine fusion with instrumentation. The primary aim of this study is to compare differences in estimated blood loss per fusion level (EBL/level) between groups ($\theta = \theta_{standard\ care} - \theta_{USBS}$). We aim to test the null hypothesis that the difference between groups is less than or equal to 0 ($H_0: \theta \leq 0$). Based on a previous retrospective cohort study in a similar target population[21], we anticipate the EBL/level in the proposed study will be 48 mL/level (± 30) in the USBS group (θ_{USBS}) and 72 mL/level (± 28) in the standard instrument group ($\theta_{standard\ care}$). Although there are no universally established thresholds for defining a clinically meaningful difference in

EBL/level, the investigators are confident that the 33% reduction in blood loss per level observed in the previous study is representative of a clinically meaningful reduction in blood loss ($H_+ \theta \geq 24$ or $H_+ \theta \geq 33\%$). Based on a symmetric two sided, two stage group sequential design with O'Brien-Fleming stopping criteria and an alpha level of 0.05, we determined that a sample size of 62 subjects (31 subjects per group) would provide 90% power to reject the null hypothesis of no difference between groups (See Trial Monitoring section for information about the stopping criteria). This estimate assumes a group difference of 24 mL/level and a standard deviation of ± 28 in the standard instrument group and a standard deviation of ± 30 in the USBS group. Assuming a dropout rate of approximately 15%, we intend to enroll 36 subjects per group to achieve the desired statistical power. The estimated dropout rate is based on previous studies in a similar patient population, adolescents with idiopathic scoliosis.

b. Subject Screening:

All surgical patients under the care of two high volume pediatric orthopedic surgeons will be screened for study eligibility. All patients who elect to undergo spinal surgery at Children's Hospital Colorado under the care of the investigators of this study will be screened for study eligibility by the research coordinator (research assistant). Patients who are determined to meet the inclusion and exclusion criteria from above will be approached by the study team.

c. Enrollment and Consent:

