Patients will be randomized 1:1 into two different treatment groups using a block randomization scheme. Using the Proc Plan procedure within SAS 9.4 (SAS Institute, Carey NC), blocks will be constructed based on surgeon and patient gender. Each surgeon will have a randomization list generated, and patient assignment will be made after the informed consent process has been performed to the next assignment on the list. Randomization assignments will not be revealed to the study personnel until after the patient has been enrolled in the study so as not to unduly bias the consent process.

Blinded evaluators will be used to calculate the primary outcome variable of interest, estimated blood loss per level fused. All other study personnel, including the surgeons, will not be blinded to participant treatment assignment which is necessary to ensure the correct protocol is followed. Patients and their families will be blinded to study assignment to minimize the risk of assignment related study withdrawal. Patients and their families will not have the assignment revealed to them after the surgery as it will not affect their plan of care. If desired, treatment allocation may be revealed at the final study visit at one year following surgery.

e. Intraoperative Estimated Blood Loss

Estimated blood loss will be determined by 3 different methods. The first and primary method is to use the estimated blood loss listed on the cell saver report. This measurement is generated by the cell saver based on the blood collected. The other two methods determine blood loss through a calculation.

Method 2:

With this method, the EBL measurements will be based on the contents of the blood and fluid collection canisters as well as the volume reports generated by the cell saver system. To ensure blinding, final levels of fluid bags and canisters will be photographed by the study surgeon immediately after the procedure is complete. Photographs will be taken by the camera features from an iPhone 6. Photographs will be taken at a distance of two feet from the canisters and bags and such that the meniscus of the fluid is at eye-level with the lens. Photographs will be reviewed by blinded evaluators at two intervals, prior to the interim analysis and following final enrollment. Two blinded evaluators will be used for each measurement, and their measurements will be averaged for use in the final calculation.

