Decision/Stopping Criteria- This study will utilize a two-stage, group sequential design to monitor study progress. Under the alternative hypothesis, the two sided rejection boundaries at Stage 1 and Stage 2 were calculated according to the O'Brien-Fleming method (see Figures below). After 16 subjects per group have been enrolled, an interim analysis will be performed (Stage 1). If the standardized Z statistic representing the difference in estimated blood loss ($\hat{\theta} = \hat{\theta}_{standard\ care} - \hat{\theta}_{USBS}$) exceeds the upper or lower rejection boundary ($Z > 2.7965$ or $Z < -2.7965$), the trial will be stopped. Assuming the standard deviation of blood loss per level fused is 30 in the USBS group and 28 in the standard group, the trial will stop if $\hat{\theta} > 29.2$ mL/level or $\hat{\theta} < -29.2$ mL/level. If blood loss per level fused does not exceed the rejection bounds, the trial will continue until a total of 62 subjects have been enrolled (31 per group). At stage 2, the standardized Z statistic will be compared to the rejection bounds ($Z > 1.9774$ or $Z < -1.9774$). Assuming the standard deviation of blood loss per level fused is 30 in the USBS group and 28 in the standard group, we will conclude the USBS is superior to standard care instrument if $\hat{\theta} > 14.6$ mL/level or inferior to standard care instruments if $\hat{\theta} < -14.6$ mL/level. Sample size and stopping criteria were estimated using the RCTDesign package, R 3.1.2 (R Foundation of Statistical Computing, Vienna, Austria).

Summary of Decision Criteria - The decision criteria and potential corresponding conclusions are described in the table below.

Stage	Enrollment	Stop For Harm			Stop for Benefit		
		$\hat{\theta}_{\dagger}$	95% CI	pvalue*	$\hat{\theta}_{\dagger}$	95% CI	pvalue**
Stage 1	50%	-27.1	-42.2 to -8.55	0.005	27.1	8.55 to 42.2	0.005

Stage 2	100%	-13.9	-29.01 to 0.00	0.05	13.9	0.00 to 29.01	0.050
*Probability reject $\theta \geq 0$							
**Probability reject $\theta \leq 0$							
†Bias adjusted mean							

Figure 1. Plots of Rejection Boundaries (Red Lines) at Stage 1 and Stage 2 Relative to a Fixed Sample Design (Black Lines). 1.A Displays Rejection Boundaries on the Z Scale 1.B Displays Rejection Boundaries in Terms of EBL/level.

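### The Stage 1 mL/level bound, table row and stopping probabilities belong to a look at exactly half the information, not at the stated 16 per group, where the bound is 28.7 rather than 29.2 mL/level

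*Combined protocol and SAP*

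**What the plan says.** The Power Analysis section fixes the design: "Based on a symmetric two sided, two stage group sequential design with O'Brien-Fleming stopping criteria and an alpha level of 0.05", and "a sample size of 62 subjects (31 subjects per group) would provide 90% power to reject the null hypothesis of no difference between groups". The planning difference is 24 mL/level, with SDs of 28 (standard instruments) and 30 (USBS).

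Under Trial Monitoring, Decision/Stopping Criteria, the interim is timed by number: "After 16 subjects per group have been enrolled, an interim analysis will be performed (Stage 1"). The rule at each stage is given first on the Z scale (±2.7965, then ±1.9774) and then in mL/level (±29.2, then ±14.6). Each mL/level figure is introduced by the condition "Assuming the standard deviation of blood loss per level fused is 30 in the USBS group and 28 in the standard group".

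The Safety Monitoring text and the summary table time the same look at 50% of enrollment instead. The summary table is introduced with "The decision criteria and potential corresponding conclusions are described in the table below". It lists 27.1 (8.55 to 42.2) for Stage 1 and 13.9 (0.00 to 29.01) for Stage 2, with a footnote calling these bias-adjusted means. It has no Z column and no unadjusted bound. A further table gives interim stopping probabilities for benefit of 0.0050, 0.0729 and 0.4930 at θ = 0, 14 and 29.

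**The concern.** A stopping threshold stated on two scales should give one decision. Here the sample size, the Z bound, the SDs and the mL/level bound are all printed, and the four do not fit together at Stage 1. The Safety Monitoring text sends the independent biostatistician to this section to decide whether a threshold has been met, so the wording must be usable without interpretation.

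Two gaps in the same section add to this. The table presented as holding the decision criteria shows adjusted estimates and no thresholds. And the plan states the SDs on which the mL/level figures rest, but not what to do when the observed SDs are different, as they almost certainly will be.

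**Working it through.** **Inputs.** SDs 30 and 28, so the variance sum is 900 + 784 = 1684. Allocation 1:1. Final size 31 per group, interim 16 per group or 50%. Z bounds 2.7965 and 1.9774. All are from the Power Analysis, Randomization and Decision/Stopping Criteria sections.

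**Reproducing the plan's figures.**
- Two equally spaced O'Brien-Fleming looks at two-sided 0.05 give Z = 2.7965 and 1.9774, as printed. Power at 24 mL/level with 31 per group is 90.06%.
- Stage 2: SE = √(1684/31) = 7.370, and 1.9774 × 7.370 = 14.57, which rounds to the printed 14.6.
- Stage 1 at 15.5 per group: SE = √(1684/15.5) = 10.423, and 2.7965 × 10.423 = 29.15. With the unrounded size for exactly 90% power (30.94 per group, interim 15.47) the bounds are 29.18 and 14.59, which round to 29.2 and 14.6.
- At 15.47 and 30.94 per group, the bias-adjusted mean on the Stage 1 bound is 27.14 (interval 8.55 to 42.20) and on the Stage 2 bound 13.88 (0.00 to 29.01). These are the table's values. The interim stopping probabilities are 0.0729 at θ = 14 and 0.4932 at θ = 29 (printed 0.0729 and 0.4930).

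**At the stated 16 per group.** SE = √(1684/16) = 10.259, and 2.7965 × 10.259 = 28.69. Conversely, 29.2 / 10.259 gives Z = 2.846.

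| Stage 1 quantity | Printed | 16 per group, Z = 2.7965 |
|---|---|---|
| Bound, mL/level | 29.2 | 28.7 |
| Bias-adjusted mean (CI) | 27.1 (8.55 to 42.2) | 26.7 (8.4 to 41.7) |
| Stopping probability, θ = 14 | 0.0729 | 0.076 |
| Stopping probability, θ = 29 | 0.4930 | 0.512 |

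**Re-derived bounds.** The bound of 2.7965 itself assumes equal spacing. O'Brien-Fleming bounds for looks at 16 and 31 per group are 2.7555 and 1.9796, or 28.27 and 14.59 mL/level.

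**Effect on type I error at the planning SDs, looks at 16 and 31.** The Z rule gives 4.99%. The mL/level rule (29.2, then 14.6) gives 4.92%.

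**If the SDs differ (illustrative assumption: both 25% larger, 37.5 and 35).** The standard errors become 12.824 and 9.213. Then 29.2 is Z = 2.28 and 14.6 is Z = 1.58. Applied literally, the fixed mL/level rule would have type I error of about 12.1%. With SDs 20% smaller it would be about 1.3%. The Z rule with observed SDs does not have this problem.

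**The θ = 0 row.** The chance of crossing 2.7965 on one side is 0.0026, so 0.0052 on both sides together. The printed 0.0050 per side does not reproduce, whichever interim size is used.

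**The case against.** The best defence is that 29.2 is right for the other timing in the plan. Half of 62 is 31 subjects. With 15 on USBS and 16 on standard instruments, SE = √(900/15 + 784/16) = 10.44, and 2.7965 × 10.44 = 29.2. On that view only the phrase giving 16 per group is out of step, by half a mL/level, and with almost no consequence: the chance that the estimate falls between 28.7 and 29.2 is about 2% even if θ is 24 or 29. This stands. It locates the error as an unreconciled interim size rather than as bad arithmetic in the bound. It does not remove the error, because the sentence that sets the look says 16 per group.

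Three stronger readings are tempting, and the documents do not support them.

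- *That the mL/level figures in general are not the Z bounds.* The 14.6 is the Stage 2 bound at 31 per group, and 29.2 is the Stage 1 bound at half the information.
- *That 27.1 and 13.9 are rival thresholds.* They are footnoted as bias-adjusted means and reproduce as exactly that. Used as raw cut-offs they would give type I error of 6.2 to 6.3%, but only if a reader ignored the footnote and the thresholds printed just above. The fair criticism is of layout.
- *That the plan fails to hold 5%.* The Z rule comes first at both stages, and each mL/level figure carries its SD condition. The 12% arises only if someone sets both aside. Nor does the background range of 65 to 150 mL per level show that larger SDs are likely: it describes typical losses and gives no within-group SD.

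What the defence cannot supply is a sentence saying that Z governs when the SD condition fails. The sentence that draws the superiority conclusion is worded in mL/level.

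**Conclusion.** The plan is wrong as written at Stage 1, in a small and easily repaired way. The text sets the look at 16 per group. The mL/level bound, the table row and the stopping probabilities at θ = 14 and 29 are those of a look at exactly half the information. At 16 per group, with the planning SDs and the stated Z of 2.7965, the bound is 28.7 and not 29.2 mL/level. The practical effect is a narrow band in which two adjacent sentences disagree. At the planning SDs, type I error and power are essentially unaffected.

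The missing statement of which rule governs matters more in principle. Its cost depends on a misapplication that the plan does not direct, and on SD departures that are assumed here for illustration. It calls for a clarifying sentence and does not show that the design loses error control.

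**What to change.** 1. Reconcile 16 per group with 50% of enrollment. State one interim size, and if a percentage is kept, state of which total.
2. Recompute the Stage 1 mL/level bound, the Stage 1 table row and the interim stopping probabilities for that look. If 16 per group and Z = 2.7965 are kept, the bound is 28.7. If O'Brien-Fleming is re-derived for 16 and 31 per group, the bounds are Z = 2.7555 (28.3 mL/level) and 1.9796. In the same run, check the 0.0050 per side at θ = 0, which recomputes to 0.0026.
3. State that the Z statistic, computed with observed SDs and actual numbers, is the only decision rule, and label every mL/level figure as illustrative at the planning SDs.
4. In the summary table, show the Z bound and the unadjusted bound beside the bias-adjusted mean, and label the latter as the estimate obtained when the bound is just reached.

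The cost is protocol wording and one rerun of the boundary software. The sample size does not change.

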Estimated blood loss/level [^]
Secondary Clinical Outcomes
Intraoperative and postoperative complications (events that cause a deviation from routine care) ^{^†‡}
Probability of meeting blood transfusion criteria (see section) ^{^†}
Procedure Time (first incision to close) [^]

Demographics/Covariates (potential confounding variables)	
Age at surgery*	BMI percentile at surgery*
Gender at surgery*	Weight (kg) at surgery*
Exposure to second hand smoke*	Preoperative Lenke Classification*
Preoperative major Cobb angle*	Preoperative hemoglobin/hematocrit*
Postoperative major Cobb angle††	Postoperative hemoglobin/hematocrit†
Intraoperative use of intrathecal narcotics^	Donor hematocrit^
Vertebral levels fused^	Intraoperative use of antifibrinolytic^

Exploratory Variables	
Unplanned return to OR††	Surgical site infection†
Procedure Time^	

* Collected preoperatively or day of surgery (before surgery)

^ Collected intraoperatively

† Collected postoperatively: short term follow-up, during initial hospital stay

‡ Collected postoperatively: long term follow-up, one year postoperative

I. Description of Population to be Enrolled:

All patients with a diagnosis of Adolescent Idiopathic Scoliosis who are scheduled for spinal fusion surgery and meet the following criteria will be eligible to participate in the study:

Inclusion Criteria:

1. 10-18 years of age
2. Diagnosis of AIS
3. Scheduled for a posterior spinal fusion (without Schwab Grade II or higher osteotomy)

Exclusion Criteria:

1. Plan for a posterior column osteotomy of Schwab Grade II or higher
2. Prior spinal surgery
3. MRI abnormalities (such as syrinx and/or chiari malformations)
4. Subjects with medical comorbidities (e.g. heart, lung, kidney disease)
5. Subjects with bleeding diatheses
6. Non-idiopathic etiology for scoliosis

II. Study Design and Research Methods

a. Power Analysis

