A second potential scientific problem could be obtaining 72 study subjects (36 for each group) to consent and enroll in the study protocol. Between the two protocol surgeons, approximately 80 patients with AIS undergo PSF each year. This population is actively involved in research at this institution and study personnel have been very successful in the past recruiting this patient population for research purposes. Based on the enrollment success rate of a current randomized clinical trial, the authors expect 80% of patients who are approached regarding this study to consent for participation. This requires 90 eligible subjects to be approached in order to reach the enrollment goal of 72. As such, it is expected that enrollment is completed within 2 years of study approval.

Finally, as this study involves long-term follow-up, there is potential for subjects to become lost to follow-up. To accommodate this, our enrollment goal factors in a 10% dropout. For subjects who are lost to follow-up, two certified letters will be sent two week apart following the first missed clinic visit. If there is no response, the subject will be contacted twice by phone. If study staff is unable to contact the subject, they will be considered lost to follow-up.

d. Data Analysis Plan

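### The stopping rule ends the trial at 62 enrolled, while the power and feasibility sections enrol 72; the rule should count subjects with blood loss recorded and take 72 as the enrolment limit

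*Combined protocol and SAP*

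**What the plan says.** Three sections give the size of the trial.

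- **Power Analysis:** "we determined that a sample size of 62 subjects (31 subjects per group) would provide 90% power to reject the null hypothesis" of no difference. It continues: "Assuming a dropout rate of approximately 15%, we intend to enroll 36 subjects per group to achieve the desired statistical power".
- **Potential Scientific Problems:** this discusses the difficulty of "obtaining 72 study subjects (36 for each group) to consent and enroll in the study protocol". It then notes that "as this study involves long-term follow-up, there is potential for subjects to become lost to follow-up", and says that the enrolment goal allows for 10% dropout on that account.
- **Trial Monitoring, Decision/Stopping Criteria:** Stage 1 comes after 16 per group are enrolled. Without an early stop, "the trial will continue until a total of 62 subjects have been enrolled (31 per group"), and the Stage 2 bound is then applied.

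The Safety Monitoring text and the summary table of decision criteria place the two looks at 50% and 100% of enrolment, without saying whether the base is 62 or 72. The Data Analysis Plan specifies an intent-to-treat analysis of all randomised subjects.

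On the primary outcome, the Outcome Measures table marks EBL per level as "Collected intraoperatively". The blood-loss section states: "The first and primary method is to use the estimated blood loss listed on the cell saver report". Under Randomization and Blinding, "patient assignment will be made after the informed consent process has been performed", so it comes before surgery.

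**The concern.** Enrolment has two end-points, 62 and 72, and the documents do not reconcile them. The rule that actually ends the trial uses the smaller one. The Power Analysis adds 10 subjects expressly to protect power, and the stopping rule read literally never enrols them. Power would then depend on every enrolled subject having EBL.

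The same ambiguity affects the timing of the looks. Half of 62 is 15.5 per group, half of 72 is 18 per group, and the stated Stage 1 count is 16. It also leaves open which final count the Stage 2 bound applies to, since the intent-to-treat set could hold 31 or 36 per group.

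**Working it through.** **Inputs.** From the Power Analysis: difference 24 mL/level and SDs of 28 (standard) and 30 (USBS). From the Decision/Stopping Criteria: Z bounds 2.7965 (Stage 1) and 1.9774 (Stage 2). The variance sum is 28² + 30² = 1684. With n per group analysed, SE = √(1684/n). Power is P(Z₁ > 2.7965) + P(|Z₁| ≤ 2.7965, Z₂ > 1.9774), by numerical integration, with the interim at half the final n.

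**Step 1: reproduce the plan's figures.** At n = 31, SE = 7.370 and power at 24 mL/level is 0.9006, in line with the stated 90%. The Stage 2 cut-off is 1.9774 × 7.370 = 14.57. The table compares the plan's results with four counts analysed: 31, 36 (all 72), 27.9 (62 less 10%) and 26.35 (62 less 15%).

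| Quantity | Stated | n = 31 | n = 36 | n = 27.9 | n = 26.35 |
|---|---|---|---|---|---|
| Stage 2 cut-off, mL/level | 14.6 | 14.57 | 13.52 | 15.36 | 15.81 |
| Interim stop, θ = 14 | 0.0729 | 0.0731 | 0.0887 | 0.0640 | 0.0596 |
| Interim stop, θ = 29 | 0.4930 | 0.4943 | 0.5799 | 0.4376 | 0.4085 |
| Power, θ = 14 | 0.470 | 0.472 | 0.531 | 0.434 | 0.414 |
| Power, θ = 29 | 0.975 | 0.975 | 0.988 | 0.961 | 0.951 |

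Only 31 observations per group fits. One row does not reproduce at any n. At θ = 0 the plan gives an interim stopping probability of 0.0050 per side, but 1 − Φ(2.7965) = 0.0026 per side whatever the sample size (0.0052 for both sides together).

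**Step 2: dropout arithmetic.** 31 × 1.15 = 35.65, which rounds up to 36. In the other direction, 72 × 0.85 = 61.2, close to 62, and 72 × 0.90 = 64.8. So the 15% in the Power Analysis connects 72 with 62; the 10% in Potential Scientific Problems does not.

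**Step 3: power if 62 are enrolled and some lack EBL.** The missing rates are assumptions.

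| EBL missing | n per group | Power at 24 mL/level |
|---|---|---|
| 0% | 31 | 90.1% |
| 5% | 29.45 | 88.5% |
| 10% | 27.9 | 86.8% |
| 15% | 26.35 | 84.9% |

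With 72 enrolled and all available EBL analysed, power is 93.8% with none missing (36 per group) and 89.7% with 15% missing (30.6 per group).

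**Step 4: how much loss 72 covers.** On average, 1 − 31/36 = 13.9%. With independent losses, the chance that both groups keep at least 31 of 36 is P(Bin(36, 0.90) ≥ 31)² = 0.855² ≈ 0.73 at 10% loss.

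**Step 5: type I error with the stated bounds and the interim at 16 per group.** Two-sided alpha is 0.0493 at a final count of 26.35 per group, 0.0497 at 29, 0.0499 at 31 and 0.0504 at 36.

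**Step 6: Stage 1 cut-off.** 2.7965 × √(1684/15.5) = 29.15, which fits the stated 29.2. At the stated 16 per group, 2.7965 × √(1684/16) = 28.69.

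**The case against.** The strongest reply is that EBL is measured in theatre and read from the cell saver report, so a subject who misses the one-year visit still contributes to the primary analysis. Potential Scientific Problems ties its dropout to long-term follow-up. If that is all that dropout means, 62 enrolled gives 62 analysed, no power is lost and the point is one of wording. This largely stands as regards size. It does not remove the contradiction: the Power Analysis ties its 15% to statistical power, and because assignment precedes surgery, a withdrawal or a missing report remains possible.

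A reader might infer from Step 1 that the tables prove 62 means subjects with EBL. They do not. A trial with 62 enrolled and every EBL recorded gives the same figures. The tables show only that 31 observations per group were assumed; the reading of 62 as the number analysed needs the Power Analysis as well. Nor does Potential Scientific Problems say that 62 should remain out of 72.

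The Stage 1 discrepancy is minor. It looks like 15.5 rounded to 16, and the operative rule is the Z bound, with the mL/level value conditional on the assumed SDs.

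The plan also refers to a DSMB charter, which is not among the documents and may define the looks. It would not remove the mismatch within the protocol.

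**Conclusion.** The inconsistency is real and should be fixed. The stopping rule as written drops an allowance that the Power Analysis says is needed. The cost is between 0 and 5.2 points of power (90.1% down to 84.9%) over an assumed range of 0 to 15% missing EBL, with 15% as a worst case. The figures rest on the plan's own difference, SDs and bounds.

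Two stronger conclusions are tempting, and the documents support neither. One is that the trial is underpowered: no rate of missing EBL is given, and the true rate may be near zero. The other is that the error rate is compromised: alpha stays between 0.0493 and 0.0504 over the counts considered. Confidence is high for the contradiction itself and conditional for any loss of power.

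**What to change.** 1. In the Decision/Stopping Criteria, define Stage 1 and Stage 2 by subjects with primary EBL recorded: 16 and at least 31 per group. Replace 62 enrolled with 72 as the enrolment limit.
2. Analyse all randomised subjects with EBL using the same Z bounds (two-sided alpha 0.0497 to 0.0504 for an interim at 16 and a final count of 29 to 36 per group). If 72 is reached before both groups have 31, analyse those available; 72 covers up to 13.9% missing on average, but this is not guaranteed.
3. State whether enrolment continues to 72 once both groups have 31 with EBL. Stopping earlier gives up the allowance for one-year follow-up described in Potential Scientific Problems.
4. State that 50% and 100% in the Safety Monitoring text and the decision table refer to these counts.
5. Give the Stage 1 mL/level cut-off for the count used (28.7 at 16 per group; 29.2 fits 15.5), and check the θ = 0 row of the interim stopping table.
6. Use one dropout figure throughout, and say whether it means missing EBL or loss to follow-up.

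If the sponsor does intend to stop at 62 enrolled, correct the 72 in the Power Analysis and Potential Scientific Problems, and state that 90% power holds only with no missing EBL.

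The cost is wording, one recomputed cut-off and one table row to check, with no patients beyond the 72 already planned.
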